3.1.4 Secondary Outcomes: Effectiveness

-Percentage with Vehicle Risks at Week 14 – We are interested to see if there is any signal of effectiveness once the intervention is "turned-off". This measure of durability is especially critical to understand potential public health benefits.

SaVE Trial Protocol v.1.0 Page **15** of **36** -Slopes of change over time – We will also examine the average slopes of change over time, specifically examining the slopes of change in the pre-enrollment, run-in (2-weeks), active intervention (6-weeks), and post-intervention (6-weeks) periods.

3.2 Rationale for Primary Outcomes

3.2.1 Overview

We chose to measure self-reported outcomes because objective data on vehicle safety behaviors is difficult to collect, costly, and obtrusive. For example, seat belt use would require in-vehicle equipment or camera monitoring. Alcohol use would require an individual to provide semi-continuous breath alcohol measurements. We chose to assess outcomes over a 2-week timeframe to minimize recall biases associated with longer recall periods but to allow an adequate sampling period where an individual had enough vehicle trips to be considered representative of behaviors. *For list of outcome assessment questions, see Appendix.*

3.2.2 Cohort 1: Any vehicle trip in past 2 weeks where individual reports not using a seat belt. Not wearing a seat belt is associated with higher odds of death or serious injury related to a motor vehicle crash. The SMS intervention aims to encourage consistent use of a seat belt. We will explore whether differences exist between front and rear-seat passenger trips or driver versus passenger trips.

3.2.3 Cohort 2: Any vehicle trip in past 2 weeks where individual reports phone was used to type while driving and car was moving. Typing while driving (TWD) has been shown to increase collision or near-collision event risk by two-fold (Fitch et al., 2013), and studies among younger drivers have found that TWD is associated with 35% slower reaction times (Reed and Robbins, 2008) and a four-fold increase in time spent looking away from the road compared to those driving undistracted (Hosking et al., 2006). We chose to asses not just typing text messages, but any typing on a phone, as there are a number of platforms for communication outside of texting that are commonly used (e.g. Google searches, social media messaging, location-based services).

3.2.4 *Cohort 3*: Any vehicle trip in past 2 weeks where individual reports driving a vehicle within 3 hours of consuming 3 or more drinks. The risk of a motor vehicle crash increases exponentially with elevated blood alcohol content (NHTSA). We chose as an outcome driving a vehicle within 3 hours of consuming 3 or more drinks as this would indicate a high likelihood of a peak BAC of at least 0.05 mg/dl, which would indicate some psychomotor impairment and elevated risk taking (Van Dyke & Filmore, 2017).

3.3 Safety

3.3.1 Overview

We do not expect, based on the nature of the SMS intervention, to have any serious adverse events. The only forseeable rare adverse event would be to cause a vehicle crash by texting with someone when they are driving. We will minimize this risk by informing all participants to refrain from texting us while driving.

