2.14 Outcome Assessments & Blinding

The primary outcomes will be the percentage of participants in each treatment arm who report vehicle risks at week 8 (immediate effects) and week 14 (durable effects). Questions are the same as those used in screening. Participants will receive a text prompting them to log in to the secure web site to complete the 21-question survey which should take them no more than 10 minutes to complete. Research associates and investigators will be blinded to the allocation until outcome evaluation. It is not possible to blind subjects given the nature of the intervention. We do not expect any scenarios where emergency unblinding will be necessary.

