3.3.2 Specific adverse event data collection

To assess specific and potentially serious adverse events that may be related to the interventions, we will collect data on the following:

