3.3.3 Adverse Event Reporting

Any unexpected adverse events will be recorded and reported directly to the appropriate IRB shortly following the event per local protocol.

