5. DATA COLLECTION AND MANAGEMENT

5.1 Data collection process

Data collection will be the responsibility of the individual site investigators with oversite from the trial coordinating center. All baseline and outcome variables (i.e. demographics, vehicle risk behaviors) will be obtained prospectively from electronic surveys. Data will be entered directly into the online database software (see below).

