Questi Sometimes when I feel bad, I can't seem to stop what I am doing even on though it is making me feel worse.						
Questi on When I am upset I often act without thinking.						
Questi on When I feel rejected, I will often say things that I later regret.						
On l generally like to see things through to the end.						
Questi on Unfinished tasks really bother me.						
Once I get going on something I hate to stop.						
on Questi I finish what I start.						
Questi on My thinking is usually careful and purposeful.						
On on I like to stop and think things over before I do them.						
$\underset{on}{^{Questi}}$ I tend to value and follow a rational, "sensible" approach to things.						
on Questi I usually think carefully before doing anything.						
Questi on I quite enjoy taking risks.						
Questi I welcome new and exciting experiences and sensations, even if they are on a little frightening and unconventional.						
on Questi I would like to learn to fly an airplane.						
Questi I would enjoy the sensation of skiing very fast down a high mountain on slope.						
Questi When I am in great mood, I tend to get into situations that could cause me on problems.						
Questi on I tend to lose control when I am in a great mood.						
Questi Others are shocked or worried about the things I do when I am feeling on very excited.						
Questi on I tend to act without thinking when I am really excited.						
Questi on How long have you been driving a car?	Less than 6 months	6 months to 1 year	1-2 years	2-5 years	More than 5 years	never driven
Code long_dr Questi How many times in the last 12 months have you received a traffic ticket? on (Not including parking tickets)	0	1	2	3	4	5
Code tix	#					
Questi on As a driver of a car, have you been in a crash in the past 12 months?						
Code crash	#					
Questi How many days over the last month have you drank more than (3 drinks on for women/ 4 drinks for men)?						

Code Imbinge

#

Questi How many days over the last month have you used cannabis (marijuana, on pot, has, grass, etc)?

Code Imbinge

#

Thanks, This ends your baseline survey. Please hand me back to the Researcher.

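### The one harm the protocol foresees, a texting-related crash, is not asked about systematically after randomisation and has no planned summary by arm

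*Combined protocol and SAP*

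**What the plan says.** Section 3.3.1 names a single foreseeable harm: "The only forseeable rare adverse event would be to cause a vehicle crash by texting with someone when they are driving". The same paragraph also states: "We do not expect, based on the nature of the SMS intervention, to have any serious adverse events". It adds that all participants will be told not to text the study while driving.

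Section 3.3.2 announces specific collection: "To assess specific and potentially serious adverse events that may be related to the interventions, we will collect data on the following". No list follows in the supplied text. Section 3.3.3 gives the recording rule: "Any unexpected adverse events will be recorded and reported directly to the appropriate IRB shortly following the event per local protocol".

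The baseline questionnaire in the appendix asks: "As a driver of a car, have you been in a crash in the past 12 months". For follow-up, section 2.14 says: "Participants will receive a text prompting them to log in to the secure web site to complete the 21-question survey". Both follow-up forms are printed in the appendix.

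Sections 4.2.1 to 4.2.5 cover the primary, secondary, missing-data and subgroup analyses and the stopping criteria. None of them mentions adverse events or a safety comparison between arms.

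**The concern.** The foreseen harm works through study texts, and the arms differ in how many they get. Control participants receive weekly assessments only (section 2.13). Intervention participants receive a weekly check-in with feedback and a goal dialogue, and the seat belt and typing scripts add messages on two random days a week. Cohort 2 is recruited because its members type while driving, a behaviour that section 3.2.3 links to a two-fold risk of a collision or near-collision.

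If nobody is asked about crashes after randomisation, a final report of none could mean that none happened or that none was volunteered. Volunteered reports may also differ by arm, because the intervention arm has more contact with the program. The departmental committee in section 7.2 is asked to watch for risks that could justify ending the study early, yet no regular supply of crash data to it is described.

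**Working it through.** **1. Is a crash item in the follow-up forms, or could one have been lost from the text?** Counting the printed items:

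- 14-week form: 8 on exposure and behaviour, 5 on seat belts, 4 on typing, 4 on drink driving. 8 + 5 + 4 + 4 = 21.
- 8-week form: the same 21, plus 3 on the program (helpful, recommend, comments). 21 + 3 = 24.

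The 21 core items match the length stated in section 2.14, so it is unlikely that a crash question dropped out of the text. None of the items asks about a crash. The printed run-in and intervention SMS scripts have no crash question either.

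**2. Does the recording rule cover the foreseen event?** Setting the safety sections side by side:

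- Section 3.3.1 calls a texting-related crash foreseeable, and section 3.3.3 records unexpected events. On that reading the crash is not covered.
- Section 3.3.1 also expects no serious adverse events. On that reading a serious crash is unexpected and is covered, while a minor one remains doubtful.

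The wording allows both readings, so two sites could treat the same event differently.

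**3. How different is exposure to texts?** In the seat belt and typing scripts, messages go out on 2 random days a week over the 6-week intervention: 2 × 6 = 12 contact days per person that control does not have. The weekly feedback and goal exchanges come on top.

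**4. How many people would answer a crash item?** Inputs from section 4.1 are 300 enrolled in Cohort 1, 10% lost in run-in, and 80% completing week 8.

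- Cohort 1: 300 × 0.90 × 0.80 = 216, or 108 per arm. This reproduces the plan's figure.
- Cohort 1 randomised but without a week-8 form: 300 × 0.90 − 216 = 54.
- All cohorts, assuming the same attrition throughout: 500 × 0.90 × 0.80 = 360, or 180 per arm.

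**5. What would zero reported crashes show?** With no events among n respondents, the one-sided 95% upper bound is 1 − 0.05^(1/n). The upper limit of the two-sided exact 95% interval is 1 − 0.025^(1/n).

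- n = 108: 2.7% one-sided, 3.4% two-sided.
- n = 180: 1.7% one-sided, 2.0% two-sided.

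**6. Could the arms be compared formally?** The documents give no crash rate, so I assume a control risk between 0.5% and 5%. With 108 per arm, the expected control-arm count is 108 × 0.005 = 0.54 to 108 × 0.05 = 5.4. Power to detect a doubling in a two-sided 5% test of two proportions is Φ{[d√n − 1.96√(2p̄(1 − p̄))] / √(p₁(1 − p₁) + p₂(1 − p₂))}, where d = p₂ − p₁ and p̄ is the mean of the two risks.

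- 0.5% vs 1%: about 6%.
- 5% vs 10%: about 29%.

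The normal approximation is rough at such counts, but the conclusion is clear: the item would support description, not a test.

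**The case against.** The strongest reply is that the plan has other routes to crash data. Section 13 gives adverse event collection to the principal investigator and the co-investigators. Section 6.2.2 has incoming messages archived and reviewed at least every 2 days. Section 7.2 has a departmental audit at least monthly. Section 3.3.2 promises a list of specific events, and that list may have been lost when the text was extracted. A reader might infer from the survey forms that the trial cannot count crashes at all. The documents do not support that: volunteered crashes could be recorded, and a lost list might name crashes with its own collection route. What still stands is that no question, schedule or case definition for crashes appears in the documents, and volunteered reports are neither systematic nor neutral between arms.

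A reader might also take section 5.1 to make surveys the only source of safety data, because it says that variables "will be obtained prospectively from electronic surveys". The subject of that sentence is baseline and outcome variables, with demographics and risk behaviours as the examples. It does not address adverse events.

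Finally, crashes are likely to be rare, section 2.16 describes the trial as minimal risk, and participants are told not to text while driving. All of this is fair. It limits what a crash item can show, as step 6 of the working makes plain. It does not remove the reason to ask about the only harm the protocol names.

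**Conclusion.** The point holds as a gap in ascertainment and reporting. The documents show no systematic, arm-neutral collection of crashes after randomisation and no planned summary by arm. They also leave unclear whether a foreseeable crash must be recorded. A reader might go further and say that section 3.3.3 excludes crashes. That is only one of two readings, and the two sections need reconciling.

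With the item added and no crashes reported, the one-sided bound would be about 2.7% per arm in Cohort 1. The 1.7% figure for all cohorts rests on applying Cohort 1 attrition to Cohorts 2 and 3, for which section 4.1 gives none. Pooling all 360 completers would give about 0.8%, since 1 − 0.05^(1/360) = 0.0083, but that figure combines the arms and says nothing about the difference between them. All these bounds assume honest self-report and apply only to people who return the survey.

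The primary analysis is not affected. This is a cheap improvement that bears on patient safety.

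**What to change.** 1. Add a crash item to the 8-week and 14-week surveys, covering the period since enrollment or since the last survey completed. Add a second item on whether a study text was being read or sent at the time. The two-week recall used for the behaviour items would leave most of the follow-up uncovered.
2. Reword section 3.3.3 so that adverse events are recorded whether or not they were expected. Keep IRB reporting as a separate sentence that follows local rules. The present sentence joins recording and reporting, so simply deleting the word unexpected would also widen what must be reported.
3. Confirm that the list belonging to section 3.3.2 agrees with both changes.
4. Add to section 4.2 a table of crash counts by arm, with the number who answered and exact 95% confidence intervals, labelled as descriptive.

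The cost is two short survey items, a few changed sentences and one table. The limits are self-report and no answers from people who do not complete the survey: 54 of the 270 randomised in Cohort 1 at week 8 on the plan's own assumptions, possibly including anyone badly hurt. The spontaneous reporting routes should therefore stay in place.

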2.16 Regulatory Issues

We will submit an IRB protocol both for the trial and coordinating center at the University of Pittsburgh. We will also submit an IRB protocol at the University of Pennsylvania. We expect the trial to be minimial risk to participants, given that the only possible risk will be from potential breach of confidentiality. We will minimize these risks through various strategies. The trial will be registerted on ClinicalTrials.gov.

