4.2.2 Primary Analysis

At baseline, all participants (based on screening criteria) all had the risk factor. At subsequent time points, participants are analyzed as having/not having the same risk factor by randomized group. For our primary analysis, we will examine the proportion of participants in each group (SMS intervention; assessment control) who report the risk behavior using a chi-squared test of proportions. We will then perform a logistical regression, entering any baseline attribute that has univariate association with the outcome in the final model. We will report the difference in percentage with primary outcomes as well as odds ratios (from logistical regressions) with 95% confidence intervals The α level is set at .05 for all statistical tests.

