Day & Time Incoming Outgoing Enrollment Hi [_NAME_]. Welcome to to the SaVE Study For the next 2 weeks, each Sunday, we will ask you about your seat belt use in the past week If you complete at least 50% of the text queries, you will be eligible for the rest of the study Any If at any time you wish to stop receiving texts, just text us "stop" response Sunday, 4pm Hi [_NAME_], it's theSaVE Team checking in How often have you been a passenger or driver in a car the past week? 0=never; 1=a few times; 2=most days; 3=every day [Missing] We missed your response. Text us how often you have been a passenger or driver in a car the past 2 hours x1 week [Missing] 2 hours х2 You must be busy. We will check in next week [Nonsense We don't understand. Please text us a response option: 0=never; 1=a few times; 2=most days; 3=every 1 day 0 ΟK 1,2,3 How often did you wear a seat belt? 0=never; 1=a few times; 2=most of the time; 3=every time [Missing] 1 hour x1 We missed your response. Text us how often you wore a seatbelt [Missing] 1 hour You must be busy. We will check in next week x2 We don't understand. Please text us a response option: 0=never; 1=a few times; 2=most of the time; [Nonsense 3=every time 1 0,1,2,3 Thanks Day 15 Due to your low response rate, you will be withdrawn from the SaVE Study (Monday) For further information about seat belt safety, go to www.NHTSA.gov

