Appendix: SMS Interventions: TWD Safety

	Incomi	
Day & Time	ng	Outgoing
Qualified Week 3, Monday, 5pm		
Qualified [At least 1 Sunday Assessment complete]		Congratulations [Name]! You have qualified to continue the SaVE Study
· · · · · · · · · · · · · · · · · · ·		For the next 6 weeks, we will help you set goals and provide you personalized feedback on your driving safety
		We will check in next Sunday. Until then, take care.
Week 3-8: Sunday, 3pm		
2 hours	[Missin g] x1	Hi [_NAME_], it's the SaVE Study Team checking in. How often have you driven a car the past week? 0=never; 1=a few times; 2=most days; 3=every day We missed your response. Text us how often you have been a passenger or driver in a car the past week?
2 110013	[Missin	car the past week:
2 hours	g] x2 [Nonse nse]	You must be busy. We will check in tomorrow. We don't understand. Please text us a response option: 0=never; 1=a few times; 2=most days; 3=every day
1 hour	0 1,2,3 [Missin g] x1	OK. When driving, how often did you type on your phone when the car was moving? 0=never; 1=a few times; 2=most of the time; 3=every time We missed your response. Text us how often did you type on your phone while the car was moving
Thou	[Missin	was moving
1 hour	g] x2 [Nonse nse]	You must be busy. We will check in tomorrow. We don't understand. Please text us a response option: 0=never; 1=a few times; 2=most of the time; 3=every time
If Goal Not Set	0	[Posiitve Reinforcement Message]
	1,2,3	[Social Norms Message]
If Goal Set	Goal met Goal	[Goal Met Message]
	not met	[Goal Not Met Message]
		Would you be willing to commit to a goal to refrain from typing on your phone while driving this week?
1 hour	[Missin g] x1 [Missin	We missed your response. Text us whether you'd be willing to set a goal?
1 hour	g] x2 [Nonse	You must be busy. We will check in later.
	nse]	We don't understand. Please text us either yes or no
No Goal	No	[No Goal Roll Library Message]
Goal +	Yes	[Goal Reinforcement Message]
Random 2 days per week, 4pm		
lf goal -		[Distracted Driving Info Message]
If goal +		[Goal Reminder Message]

SaVE Trial Protocol v.1.0 Page **31** of **36**

Incoming	Outgoing
	Congratulations [Name]! You have qualified to continue the SaVE Study
	For the next 6 weeks, we will help you set goals and provide you personalized feedback on your driving safety
	We will check in next Sunday. Until then, take care
	Hi [_NAME_], it's the SaVE Study Team checking in

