Appendix: 8-Week Assessment

	been in a car over the past 2 weeks.				
Questi on	How often have you driven a car?	Never	A few times	Most days	Every day
Code	driver	0	1	2	3
Questi on	How often did you wear a seat belt when you drove a car?	Never	A few times	Most of the time	Always
Code	drive_seatbelt	0	1	2	3
Questi on	How often have you been a passenger in the front seat of a car?	Never	A few times	Most days	Every day
Code	pass_front	0	1	2	3
Questi on	How often did you wear a seat belt when you were a passenger in the front seat ?	Never	A few times	Most of the time	Always
Code	pass_seatbelt1	0	1	2	3
Questi on	How often have you been a passenger in the back seat of a car?	Never	A few times	Most days	Every day
Code	pass_back	0	1	2	3
Questi on	How often did you wear a seat belt when you were a passenger in the back seat?	Never	A few times	Most of the time	Always
Code	pass_seatbelt2	0	1	2	3
Questi on	How often did you type on your phone while you were driving and when the car was moving?	Never	A few times	Most of the time	Always
Code	distract	0	1	2	3
Questi on	What's the most number of alcoholic drinks you've had prior to driving on any occasion?	#			
Code	drinks	#			

The following questions ask you to recall times you have been in a car over the past 2 weeks.

Questi on	Check off all the reasons you have not used a seat belt	Uncomfort able	Forgot	Don't think they help	Like freedom	Other	l alway s wear my seat belt	
Code	seatbelt reasons	0	1	2	3	4	5	
Questi on	lf other, state reasons							
Code	seatbelt_other							
Questi on	How often do your friends use their seat belt?	Never	Rarely	Most of the time	Always			
Code		0	1	2	3			
Questi on	How dangerous is it to not wear a seat belt?	Not at all	Somew hat	Very	Comple tely			
Code	danger_seatbelt	0	1	2	3			
Questi on	How much do you agree: I have complete control over whether I wear a seat belt.	Strongly Disagree	Disagre e	Somew hat Agree	Mostly agree	Stron gly Agree		
Code	control_sb	0	1	2	3	4		
Questi on	Check off all the reasons you have typed on your phone while driving?	l could not wait	l don't think it affects my driving	It was an emerge ncy	It is fun	l get bored drivin g	l do not use my phon e while drivin g	l do not dri ve
Code	twd reasons	0	1	2	3	4	9 5	6
Questi on	How often do your friends type on their phones while driving?	Never	Rarely	Most of the time	Always			
Code		0	1	2	3			

SaVE Trial Protocol v.1.0 Page **33** of **36**

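### Typing while driving, the route to the plan's only foreseen adverse event, is compared by arm only in Cohort 2; the promised warning is in no displayed welcome, query or reminder text; and section 2.16 conflicts with 3.3.1.

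*Combined protocol and SAP*

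**What the plan says.** **Risk.** Section 3.3.1 states: "The only forseeable rare adverse event would be to cause a vehicle crash by texting with someone when they are driving". The mitigation follows: "We will minimize this risk by informing all participants to refrain from texting us while driving". No channel, wording or timing is given. Section 2.16 tells the IRB that "the only possible risk will be from potential breach of confidentiality".

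**Scripts.** The three run-in welcome texts give the schedule, the response rule ("If you complete at least 50% of the text queries, you will be eligible for the rest of the study") and the stop instruction ("If at any time you wish to stop receiving texts, just text us", followed by the keyword). The weekly queries and the 1- and 2-hour reminders ask for replies and say nothing about driving. The nearest wording is in the Cohort 2 intervention script: "Would you be willing to commit to a goal to refrain from typing on your phone while driving this week". That is an optional goal about typing in general, put to one arm of one cohort.

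**Measurement and analysis.** The screening form and the single week 8 and week 14 forms all ask "How often did you type on your phone while you were driving and when the car was moving" (item `distract`, scored 0 to 3). Under section 4.2.2, "participants are analyzed as having/not having the same risk factor by randomized group". The synopsis and section 3.1.1 define that risk factor cohort by cohort. The other between-arm analyses in 4.2.3 concern perceived norms, control and risk, and the slope of SMS risk reports, which cover only the target behaviour.

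**The concern.** The intervention works through the participant's phone, and its arm receives more texts than control. If those texts raise phone use at the wheel, seat belt use could improve while another crash risk worsens. Section 3.2.3 itself cites a two-fold increase in collision or near-collision risk from typing while driving.

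Cohort 2 is the wrong place to look for this, because there the intervention tries to lower the same behaviour and could mask an increase. Cohorts 1 and 3 are the informative ones. They will include people who type while driving: section 2.7 sends to Cohort 1 75% of those with seat belt risk plus one other risk, and 60% of those with all three. The data will be in hand, but no comparison is planned.

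**Working it through.** **1. The plan's own sample size.** Section 4.1 gives 25% v 10%, two-sided alpha 0.05 and 80% power.

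n per arm = [1.96 × √(2 × 0.175 × 0.825) + 0.842 × √(0.25 × 0.75 + 0.10 × 0.90)]² / 0.15² = 99.5, so 100.

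This agrees with the plan. Attrition: 300 × 0.9 × 0.8 = 216, or 108 per arm, also as stated.

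**2. Share of participants left uncompared.** The plan gives attrition for Cohort 1 only; I assume the same elsewhere.
- Cohorts 2 and 3: 100 × 0.9 × 0.8 = 72 each, or 36 per arm.
- Total: 216 + 72 + 72 = 360.
- Typing while driving compared by arm: 72 of 360 (20%). Not compared: 216 + 72 = 288 (80%).

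**3. Text exposure by arm.** These are counts from the seat belt script, for a week in which the participant rode in a car and answered everything.
- Intervention: greeting, two queries, feedback, goal question and goal response make 6. Two random-day texts bring it to 8. Replies requested: 3.
- Control: greeting, two queries and thanks make 4. Replies requested: 2. This assumes the run-in script continues, since no separate control script is shown.
- Over six weeks: 8 × 6 = 48 v 4 × 6 = 24 texts, and 3 × 6 = 18 v 2 × 6 = 12 replies, before reminders.

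**4. Precision of the missing comparison.** The documents give no rate of typing while driving, so prevalence p is assumed equal in both arms. Half-width of the 95% CI = 1.96 × √(2p(1−p)/n).

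| Cohort | n per arm | p = 0.3 or 0.7 | p = 0.5 |
|---|---|---|---|
| 1 | 108 | 12.2 points | 13.3 points |
| 3 | 36 | 21.2 points | 23.1 points |

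At p = 0.1 the half-widths are 8.0 and 13.9 points. Over assumed control rates of 10% to 60%, power to detect a 10-point rise is about 31% to 54% in Cohort 1 and 13% to 22% in Cohort 3.

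**5. Timing.** The intervention runs in weeks 3 to 8, so the two-week recall at week 8 falls inside it. Sections 2.12 and 2.13 put both arms on assessments alone after that, so at week 14 planned text exposure is equal.

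**The case against.** **No broken promise is shown.** A reader might infer that participants are never warned. The documents do not support that. Section 3.3.1 names no channel; section 6.2.1 has the research associate describe procedures and risks orally and in writing; and the consent pages are not in this copy. The bracketed feedback, information and reminder messages are not reproduced, nor is a control script for weeks 3 to 14. What stands is narrower: the welcome, query and reminder texts that are shown lack the warning.

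**Pressure to reply is modest.** Each unanswered query gets one reminder and then a closing message. The 50% rule applies in the run-in, before randomization and alike in both arms, so it cannot create an arm difference. This is accepted; the difference between arms comes only from the extra intervention texts.

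**The measure is weak.** `distract` captures any typing over two weeks, not replies to the study. It has no option for people who did not drive, and Cohort 1 includes passengers. The intervention adds only one requested reply per week, because the random-day texts show no request. All of this stands. It argues for an estimate rather than a powered test, but not for leaving the data unexamined.

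**Safety collection may be fuller than it looks.** The list promised in section 3.3.2 is blank in this copy and may have been lost in extraction. It cannot be concluded that crashes go uncollected.

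**The outcome wording might cover all risks.** Sections 2.14 and 3.1.4 speak of vehicle risks in general, but the synopsis, 3.1.1 and 4.2.2 tie the outcome to each cohort's own behaviour.

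**Conclusion.** The point holds in three limited parts. Sections 2.16 and 3.3.1 contradict each other. The promised warning is absent from every displayed welcome, query and reminder text, though it may be given elsewhere. Typing while driving is collected in all cohorts, but a comparison by arm is specified for only about 72 of 360 analysed participants, in the cohort least able to reveal an unintended increase.

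The 360 rests on the plan's Cohort 1 attrition applied to all cohorts; the precision figures rest on assumed prevalence. Nothing in the documents shows that the intervention raises typing while driving, and the primary analysis is unaffected. These are inexpensive improvements that the plan should make. The added comparison would be imprecise, particularly in Cohort 3, so a null result must not be read as evidence of safety.

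**What to change.** 1. Add one sentence to the welcome text and to the Sunday check-in greeting in both arms of all cohorts, such as *Please do not read or answer our texts while driving*. This carries out 3.3.1 at the point where replies are requested. It assumes that controls keep receiving the run-in greeting. Small downside: in Cohort 2 the sentence touches the target behaviour, though equally in both arms.

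2. Add to section 4.2.3 a by-arm comparison of `distract` > 0 at week 8, reported as a difference with 95% CI and not as a powered test. Cohort 1 is the primary safety estimate and Cohort 3 is descriptive. Count participants who did not drive (`driver` = 0) as not typing. Show week 14 descriptively only. The SMS substitution for missing outcomes cannot be used here, because Cohorts 1 and 3 are not texted about typing; report the number missing by arm. State that the item is a proxy.

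3. Reconcile 2.16 with 3.3.1, and say where else the warning is given. Check section 6.1 at the same time, since it does not list a crash either.

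The cost is one sentence in the scripts, one table from data already collected and a wording correction. No new participants, visits or survey items are needed. Section 2.12 has the scripts written before enrolment, so the sentence belongs there from the start.
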